**Power Analysis**

In the Dreyfuss et al prospective cohort study of conventional RFA for the treatment of chronic lumbar facet joint pain, which used an identical diagnostic/selective MBN block protocol (SIS guidelines), to that of the proposed study, 87% of patients experienced at least 60% reduction in pain at 10-month follow-up. For the present power analysis, we will more conservatively estimate a success rate of 80%, using 50% relief in pain at 3 months as the definition of success.

No study to date has used dual comparative MBN blocks to select patients for facet joint injection of corticosteroid. However, Carette et al. used intra-articular injection of local anesthetic only (>50% relief considered “positive) in order to select patients for a randomized controlled trial of lumbar facet joint injection of corticosteroid versus saline. In this study, a 42% success rate was observed at 3 months. For the present power analysis, we will more conservatively estimate a success rate of 50% at 3 months, as participants will be selected by dual comparative MBN blocks rather than only one intra-articular diagnostic injection.

Given that the primary analysis will be categorical in nature (comparison of the proportion of responders), with an alpha level of 0.05 and a power of 0.80, 39 participants would be needed in each group (total 78 participants) to detect a significant difference in the proportions between the two groups (80% vs. 50%) using a chi-square test. However, in order to improve the power of the study beyond the minimally acceptable standard and to account for anticipated attrition, we propose to enroll 135 patients in the trial.

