### *Baseline & Follow-up:*

- Percentage of relief with each of the MBN block procedures (from pain diary)
- NPRS back pain (7-day average)
- Current NPRS
- Oswestry Disability Index score
- PROMIS Physical Function Computer Adaptive Test (PF CAT) score
- PROMIS Global short-form 10 (Global-10) score
- Opioid and non-opioid analgesic use
- Ancillary treatment log

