## **Study Timeline**

### *Baseline:*

Participants who meet inclusion and exclusion criteria will be enrolled into the study after consenting to and before receiving treatment. The baseline examination and all baseline questionnaires will be completed within 8 weeks before the index study treatment procedure (facet joint steroid injection or medial branch radiofrequency ablation) as time is needed to obtain insurance authorization for all study procedures in the present study (all procedures in this

study represent usual care procedures: medial branch blocks, facet joint injections, and medial branch radiofrequency ablation).

*Follow-up:*

Routine scheduled follow-up will occur at 1 month (+/- 2 weeks), 3 months (+/- 4 weeks), 6 months (+/- 6 weeks), 12 months (+/- 3 months), and 24 months (+/- 3 months), at which times all follow-up measures will be obtained.

The 3-month follow-up will serve as the time point for the primary outcome analysis of the randomized trial and an intention-to-treat analysis will be used to evaluate for differences in outcomes between the two groups. The 3-month time point provides a reasonable timeframe to evaluate the clinical effects of the lumbar MBN C-RFA while also providing a humane timeframe for crossover to active treatment in those randomized to usual treatment. All subsequent follow-up periods are intended to evaluate long-term clinical outcomes of lumbar MBN C-RFA and will be evaluated with an as-treated analysis.

The study start date and the outcome assessment timeline will begin at the date of the participant's initial facet-targeted treatment. After 3 months, patients who have failed treatment (not meeting criteria for success, as described above) can be offered alternative treatment. Those who cross-over will be considered treatment failures of the original treatment, by definition, and continue on the regular follow-up schedule. A new 2-year follow-up period will begin upon cross-over.

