#### *FJI Procedure (Procedure as performed as standard of care clinical practice)*

During the C-RFA procedure, the participant will be positioned prone on a fluoroscopy table. Sterile precautions, including sterile preparation, drapes, and gloves, will be undertaken.

Using an oblique fluoroscopic view, the image intensifier will be rotated to optimize the posterior joint space opening. A spinal needle will be advanced under fluoroscopic guidance to enter the posterior joint space. The needle position will be confirmed in both AP and oblique views. Approximately 0.2-1 mL of iodinated contrast medium will be injected to confirm intra-articular placement and no vascular uptake. The injection will be then completed with 0.5 mL of 40mg/mL Kenalog and 0.5 mL of 1-4% preservative-free lidocaine. This technique will be repeated for each facet joint injected.

For bilateral low back pain, a maximum of 4 facet joints (two on each side) will be injected. For unilateral low back pain, up to 3 facet joints will be injected.

*Group Assignments:*

Patients will be randomly assigned to the two treatment groups (C-RFA vs. FJI) at a 1:1 ratio. Participants who reported 50% or more relief of their usual pain (NPRS score compared to baseline) at the 3-month follow-up time point and who subsequently experience a treatment effect that diminishes by > 50% will be offered a repeat procedure. Duration of relief will be considered the time from the provision of the treatment procedure until the participant returns to 50% of their pre-treatment level of pain as reported during scheduled follow-up, or when a repeat treatment procedure is requested and performed.

*Crossover:*

Any time after the 3-month follow-up, any participant who has not obtained adequate pain relief can ask to cross over to alternative treatment group. In doing so, a new 2-year follow-up will begin for this participant who is now placed in the alternative treatment group for the long-term, as-treated outcomes analysis.

*Co-interventions:*

Patients are allowed to receive usual care, including co-interventions, as deemed necessary by the treating physician. Treatments related to the participant's spine condition will be reported on the ancillary treatment log.

*Primary Outcomes:*

The primary outcome for the randomized trial is the proportion of responders, defined by a reduction in NPRS score  $\geq 50\%$  at the 3-month follow-up.

*Secondary Outcomes:*

1. Physical function (ODI and PF CAT)

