### **Data Analysis**

Results of the randomized comparative trial will be determined by an analysis of categorical data from the 3-month follow-up. At 3-month follow-up, prior to allowing crossover, overall treatment response rates (in the previously defined categories of failure or success) will be calculated for both treatment groups using an intention-to-treat analysis. For time periods beyond 3 months, intention-to-treat and as-treated analyses will be performed with primary reporting based on the as-treated analysis to assess the long-term effectiveness of each treatment. In the intention-to-treat analysis, participants who cross-over will be treated as treatment failures of their original group assignment. In addition, a treatment benefit survival analysis will be performed.

Subgroup analyses will be performed to assess treatment response and long-term effectiveness in patients reporting 100% relief from lumbar MBN blocks as compared with those reporting between 80% relief. Data will also be examined to identify any factors that predict treatment success and need for repeat treatment.

Secondary outcomes will be similarly evaluated. For the assessment of function and global quality of life, the proportions of those achieving and not achieving the established minimal clinically important differences (MCID) will be determined and compared between the two treatment groups at the 6-month follow-up. For long-term analysis of treatment effectiveness, an as-treated analysis will determine the proportion of participants exceeding these response thresholds. In addition to these categorical outcomes, changes in group mean scores will be measured and compared.

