### *Statistical Analysis*

Descriptive statistics and graphical displays will be used to examine the central tendency and distribution of each outcome variable. Data will be analyzed using Stata (ver. 14.2, StataCorp LLC, College Station, TX, USA). An alpha level of 0.05 and two-tailed tests will be used for all hypothesis testing.

To illustrate the demographic, radiologic, and procedural characteristics of the study sample, means and standard deviations or medians and interquartile ranges (depending on the distribution of data) will be calculated for continuous variables, and frequencies and proportions will be calculated for categorical variables. Demographic, clinical, and radiologic differences will be compared between the groups (C-RFA vs. FJI) in order to ensure that the two groups are equal in terms of observed as well as unobserved covariates other than the treatment provided to them.

In comparing groups (C-RFA vs. FJI) with regard to categorical variables, Fisher's exact tests will be used. Proportions and 95% confidence intervals will also be calculated in order to confirm that any differences between groups are truly distinguished. A proportion ratio will be calculated as the measure of the effect size. For quantitative variables, independent *t*-tests or Wilcoxon-Mann-Whitney tests will be used to compare means or medians, respectively. An effect size of *r* will be calculated to examine the magnitude of a group difference.

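### The sample size is justified with a chi-square test but the analysis plans Fisher's exact test, whose 80% power minimum is 44 per group, not 39; continuous secondary outcomes are not adjusted for the baseline values collected

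*Combined protocol and SAP*

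**What the plan says.** The Power Analysis assumes success rates of 80% (C-RFA) and 50% (FJI) at 3 months, alpha 0.05 and power 0.80. It concludes that "39 participants would be needed in each group (total 78 participants") to detect the difference "between the two groups (80% vs. 50%) using a chi-square test". It then raises the target, partly for more power and partly "to account for anticipated attrition, we propose to enroll 135 patients in the trial". It states neither the power at 135 nor the attrition rate.

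The Statistical Analysis section makes all tests two-tailed at 0.05 and says that "with regard to categorical variables, Fisher's exact tests will be used". The primary outcome, a reduction of at least 50% in NPRS at 3 months, is categorical, and nothing exempts it from this rule.

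For quantitative variables the same section plans independent t-tests or Wilcoxon-Mann-Whitney tests. The Data Analysis section adds that "changes in group mean scores will be measured and compared". The list of measures taken at both baseline and follow-up includes "Oswestry Disability Index score", with PF CAT, Global-10 and analgesic use. No model using a baseline value as a covariate is named for the treatment comparison.

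**The concern.** The sample size rests on one test and the analysis on another, more conservative one, so the stated 80% power minimum does not belong to the planned analysis. The two tests can also disagree on the same data. If the report used chi-square because the Power Analysis names it, a reader could not tell whether that choice was made in advance.

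The margin at 135 cannot be judged from the text either. An intention-to-treat analysis is specified, and crossovers count as failures, but the plan does not say how a participant with no 3-month NPRS is classified. That rule affects power far more than the choice of test does.

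For the continuous secondary outcomes, baseline enters at most by subtraction. Precision that the collected data could give is left unused.

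**Working it through.** **Inputs.** From the Power Analysis: 80% vs 50%, alpha 0.05, power 0.80, 135 enrolled. From the Statistical Analysis: two-tailed Fisher's exact test. From Group Assignments: 1:1 allocation, taken here as 67/68 or 68/67 (C-RFA/FJI). The attrition rate and the baseline to follow-up correlation are not given, so ranges are shown.

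**1. The plan's own figure.** With mean proportion 0.65,

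n = [1.960 × √(2 × 0.65 × 0.35) + 0.842 × √(0.80 × 0.20 + 0.50 × 0.50)]² / 0.30² = 38.48,

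which rounds up to 39 per group. The figure reproduces for a two-sided chi-square test without continuity correction.

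**2. Power of the planned test.** Exact power is the sum, over all pairs of responder counts for which the two-sided test gives p ≤ 0.05, of the product of the two binomial probabilities.

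| Evaluable (C-RFA/FJI) | Fisher | Chi-square |
|---|---|---|
| 39/39 | 73.2% | 81.3% |
| 43/43 | 79.6% | 85.5% |
| 44/44 | 80.2% | 86.4% |
| 67/68 | 95.4% | 96.3% |
| 68/67 | 95.9% | 96.4% |

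The Fisher minimum with equal groups is therefore 44 per group, 88 in total. With all 135 evaluable, the choice of test costs 0.5 to 0.8 points.

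**3. Effect of losses.** The loss rates are assumptions, taken as equal in both groups.

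- *Losses excluded.* Fisher power is 92.0% to 93.3% at 10% lost (60 or 61 per group), 88.6% at 20% (54 per group) and 83.0% at 30% (47 per group). The 88 needed remain until 1 − 88/135 = 34.8% are lost.
- *Losses counted as non-responders*, with 80% vs 50% holding among those followed. At loss L the rates become 0.80(1 − L) and 0.50(1 − L); at 20% they are 64% vs 40%. Fisher power is 87.5% to 88.0% at 10% lost, 80.4% to 80.8% at 17%, 79.4% to 79.7% at 18%, and 77.2% to 77.4% at 20%. Chi-square gives 82.1% to 82.3% at 20% and crosses 80% at about 22%. Here the choice of test costs about 5 points.

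**4. Type I error.** At 67/68 with a common response rate of 50%, exact size is 3.9% for Fisher and 5.8% for chi-square. At a common rate of 65%, the midpoint of the planning rates, chi-square size is 5.0%.

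**5. Baseline adjustment.** Let ρ be the correlation between baseline and follow-up scores (not the effect size r in the Statistical Analysis section). With equal variances σ² at both times, a change score has variance 2σ²(1 − ρ) and ANCOVA has residual variance σ²(1 − ρ²). The ratio is (1 + ρ)/2.

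| Assumed ρ | Variance ratio | Change-score sample with the precision of 135 under ANCOVA |
|---|---|---|
| 0.3 | 0.65 | 135/0.65 = 208 |
| 0.5 | 0.75 | 135/0.75 = 180 |
| 0.7 | 0.85 | 135/0.85 = 159 |
| 0.9 | 0.95 | 135/0.95 = 142 |

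For a strongly skewed score, ANCOVA on the raw scale is not the right replacement. In a simulation under assumed conditions (lognormal scores with log SD 1, log-scale correlation 0.5, shift of 0.4 log SD, 67/68, 6,000 runs), power was 51.4% for raw ANCOVA, 60.4% for Wilcoxon on follow-up, 47.8% for Wilcoxon on change and 71.7% for rank-based ANCOVA. The type I error of the rank version was 4.9% (10,000 runs).

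**The case against.** The strongest reply is that the mismatch has little practical effect. Chi-square appears only in the sample-size calculation, where 39 is right; the analysis text names one test, Fisher's. Sizing by an approximate formula and analysing by an exact test is common, and the plan enrols 135, not 78. This largely stands: the trial is not underpowered with complete data, and 39 is not an arithmetic error.

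It is also fair that power below 80% at about 20% loss needs three assumptions the plan does not state: losses count as failures, losses are equal across groups, and the planning rates hold among those followed. The 5.8% chi-square size belongs to a 50% common rate and is lower at the planning midpoint.

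On baseline adjustment, change scores already use baseline, the mean comparisons supplement the MCID proportions compared at 6 months, and the gain cannot be computed from the documents. All true: this is an improvement in efficiency, not the repair of an invalid test.

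None of this removes the two points that matter. The stated minimum does not hold for the planned test, and collected baseline data go unused as covariates.

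**Conclusion.** The concern holds, as a matter of consistency, pre-specification and efficiency rather than validity. Under the plan's own rates, the 80% power minimum for the planned two-tailed Fisher test is 44 per group (88 in total), and the stated 39 per group gives 73.2%. Enrolment of 135 covers this comfortably if losses are small or are excluded. Under a non-responder rule with equal losses, the margin is gone at about 17% loss. Which situation applies cannot be told from the plan.

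For the continuous secondary outcomes, ANCOVA would cut variance by 5% to 35% relative to change scores for assumed correlations of 0.9 down to 0.3, given equal variances at the two times. The unadjusted analysis remains valid.

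**What to change.** 1. **Primary test.** Name the same test in the Power Analysis and the Statistical Analysis. If Fisher is kept, restate the minimum as 44 per group (88 in total). If chi-square is chosen, keep 39 and note that its exact size can slightly exceed 5%. Either way, keep 135 and state the power there, the assumed loss rate, and how a participant without a 3-month score is classified.
2. **Continuous secondary outcomes.** For the as-randomised comparisons of ODI, PF CAT, Global-10 and MQS III, chiefly at 3 months before crossover, use ANCOVA with the baseline value as covariate. Use a rank-based or robust version for clearly skewed scores such as MQS III, and still report a difference on the original scale. Leave the as-treated analyses as planned, since after crossover "a new 2-year follow-up will begin for this participant".
3. **Timing of the covariate.** State that it is recorded before randomisation. The Study Timeline says only that "The baseline examination and all baseline questionnaires will be completed within 8 weeks before the index study treatment procedure", which does not place it before allocation.
4. **Minor wording.** Say that the planned 95% confidence intervals are for the between-group risk difference and the proportion ratio, and do not judge differences by whether separate group intervals overlap.

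The cost is SAP wording and minor programming, with no extra patients or data. Keeping Fisher means a less favourable stated minimum and 0.5 to 0.8 points of power at 135 evaluable. Choosing chi-square gives up the guarantee that size stays at or below 5%. The gain from ANCOVA is small if the correlation is very high.

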## Budget

Please see attached.

